6.7.5 Proposed outcome and process measures

Proposed outcome and process measures for a future large scale trial will be administered on three occasions: i) T0 - before patients are randomised to the intervention or control group, ii) T1 - at the end of the intervention (data will be collected 12 weeks after baseline for patients in the control arm) and iii) T2 - 3 months later. Thus, participants will be asked to wear an accelerometer for 7 days on 3 occasions (T0 - before patients are randomised to the intervention or control group; T1 - at the end of the intervention (data will be collected 12 weeks after baseline for patients in the control arm); and T2 - 3 months later). To meet Objective 7, a researcher will log missing data.

6.7.6 Semi-structured interviews

To meet Objective 10, on completion of rehabilitation, semi-structured face-to-face interviews [52] will be conducted with 24 cancer patients with equal split between research sites and each trial arm. Twelve clinicians involved in recruitment and/or delivering the intervention split between the research sites will also be interviewed. The interviews will elicit responses about the intervention and trial procedures. All researchers involved in conducting interviews will be receive guidance and support by applicants ([name] and [name]) who are very experienced in conducting qualitative research and have expertise in conducting interviews with patients with cancer in a sensitive manner using good communication skills (e.g. showing empathy, interpreting body language).

6.7.7 Adverse event reporting

Although this is not a Clinical Trial of an Investigational Medicinal Product, the Investigators will adhere to Tayside Medical Science Centre (TASC) SOP 11, 'Identifying recording and reporting adverse events for clinical trials of investigational medicinal products' with expedited reporting to the Sponsor as required. This will be overseen by Tayside Clinical Trials Unit.

In particular the following Serious Adverse Event (SAE) will be reported within 24 hours of the PI or person delegated responsibility for recording SAEs becoming aware of them:

(SAE): any adverse event occurring that results in any of the following outcomes:

- Death:
- In-patient hospitalization or prolongation of existing hospitalization;
- Persistent or significant disability/incapacity;

The following protocol exclusions will apply: -

- Hospitalisation for assault or accidental injury
- Hospitalisation for pre-planned surgery

The above protocol exclusions will be recorded in the Adverse Event (AE) log for the trial and line listings will be reported annually to ethics and the Sponsor.

Note: Medical and scientific judgment should be exercised in deciding whether expedited reporting is also appropriate in situations other than those listed above. For example, important medical events may not be immediately life threatening or result in death or hospitalization but may jeopardize the subject or may require intervention to prevent one of the outcomes listed in the definition above. Any adverse event is considered a serious adverse event if it is associated with clinical signs or symptoms judged by the investigator to have a significant clinical impact.

It is also worth noting that each hospital and hence cardiac rehabilitation programme will have a reporting system for adverse events (e.g. Datix) and cardiac rehabilitation programme operate incident reporting.

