6.4 Intervention and control (usual care)

The intervention is rehabilitation for colorectal cancer patients in a cardiac rehabilitation setting. An 8/12-week (number of weeks depending on research site) post-hospital rehabilitation programme will be delivered by a member of the cardiac multi-disciplinary team (e.g. cardiac physiotherapist, cardiac nurse or dietician) to a mixed class of cancer/cardiac patients in a cardiac rehabilitation setting with some components specifically tailored for cancer patients and delivered by a cancer nurse. Rehabilitation classes will be delivered twice weekly or once a week depending on research site. The rehabilitation programme comprises 60/90 minutes (depending on research site) of exercise training (aerobic and muscle strengthening) delivered to a mixed class of cancer/cardiac patients by a cardiac physiotherapist who will receive additional training and on-going support by a cancer-exercise specialist.

Participants will set individual physical activity goals with advice and support from the physiotherapist. Cardiac physiotherapists will be pragmatically applying underpinning health behaviour theories by for instance, discussing barriers to engaging in physical activity with patients and goal setting, which is in line with current behaviour change theory [68-71] and cardiac rehabilitation guidance [72]. It is now well recognised that advice, education or information does not lead to lasting change in repetitive health behaviours. It is also universally accepted that increasing physical activity leads to a host of major health benefits, but while many individuals have the best of *intentions* to take more exercise, this does not translate into lasting change in *behaviour*. This is well-recognised as the intention-behaviour gap [73] and why action and coping planning is recommended and will be adopted [74].

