9. PROJECT MANAGEMENT

The responsibility for obtaining NHS ethical and local R&D management approval will lie with the Chief Investigator. The Chief Investigator will be responsible for overseeing the progress of the study. The day-to-day management of the feasibility study (Phase 1) will be co-ordinated by the Chief Investigator and the day-to-day management of the pilot RCT (Phase 2) will be co-ordinated by the Trial Manager located at the Tayside Clinical Trials Unit. Responsibility for day-to-day line management of appointed researchers will be the Chief Investigator during Phase 1 and the Tayside Clinical Trials Unit Trials Manager for Phase 2. Tayside Clinical Trials Unit will be responsible for maintaining and archival of study documentation. The Chief Investigator and Trial Manager will take responsibility for ensuring that the study abides by the policies of the Research Governance Framework for Health and Community Care (Scotland), the Data Protection Act and any other relevant legislation and regulatory guidance. All co-Investigators will assist the Chief Investigator and carry out designated tasks in accordance with the study protocol. A study steering group will be responsible for advising the Chief Investigator and Trial Manager about the study. It will meet on three occasions: at the commencement of the study, at the end of Phase 1 and at the end of Phase 2 to provide advice and guidance. This group includes the Chief and co-Investigators, a representative from colorectal cancer and cardiac rehabilitation clinical teams and two patient representatives and Operations Manager (Scotland) from Bowel Cancer UK. Site specific local Investigators are co-investigators ([name], [name] and [name]) and will be responsible for ensuring that all trial-related clinical decisions (e.g. screening for contraindications to exercise) are made and that the recruitment strategy is implemented and the research conducted in their site complies with local NHS ethics and research governance.

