10.2 Risks to participants

This is a low risk study and major risks and safety issues are not anticipated. No invasive procedures are being used in this study. The intervention includes an exercise component during the period of recovery following surgery. Moderate physical activity is recommended for colorectal cancer patients during treatment and has no contraindications for most [49]. The American College of Sports Medicine recommend that cancer patients avoid inactivity and return to normal activity as soon as possible after diagnosis and treatment and should engage in at least 150 minutes per week of moderate intensity or 75 minutes per week of vigorous intensity aerobic physical activity, or an equivalent combination of moderate and vigorous intensity aerobic physical activity [59]. Evidence suggests that it is not only feasible to exercise during the period of recovery post-surgery but that it can improve cardiovascular fitness, muscle strength, body composition, fatigue, anxiety, depression, self-esteem, and quality of life [49]. Nevertheless, effects of treatment may increase the risk of exercise-related injuries and adverse effects and so during the screening process for study participation those patients who are contraindicated for moderate intensity physical activity or who have an injury or illness which might be aggravated by exercise, will be excluded from the study:

- 1. The patient's cancer clinical team at a post-treatment follow up appointment will assess if there are contraindications to exercise due to cancer and late effects of treatment (e.g. patients with severe anaemia or with compromised immune function).
- 2. A cardiac rehabilitation clinician (e.g. cardiac nurse/cardiac physiotherapist) will conduct a clinical/risk stratification assessment to determine whether a patient can safely exercise from a cardiac clinical perspective.
- 3. During rehabilitation the cardiac physiotherapist running the exercise class will monitor patients for adverse events (e.g. chest pain, extreme breathlessness) and will decide whether it is safe for the patient to continue participation. An adverse events log will be kept for the duration of the study.
- 4. Patients will be advised and encouraged to contact their colorectal cancer Clinical Nurse Specialist if they have any questions or concerns about their health during the trial.

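### Section 6.7.7 takes accidental-injury admissions out of 24-hour SAE reporting without excepting injuries from the study exercise, so such an admission may reach the sponsor only in an annual listing

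*Protocol*

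**What the plan says.** Protocol section 6.7.7 states that SAEs "will be reported within 24 hours of the PI or person delegated responsibility" becoming aware of them. Three outcomes make an event serious: death, "In-patient hospitalization or prolongation of existing hospitalization", and persistent or significant disability.

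Two protocol exclusions follow. One is "Hospitalisation for assault or accidental injury"; the other is admission for surgery planned beforehand. Excluded events go into the adverse event (AE) log, and "line listings will be reported annually to ethics and the Sponsor". Accidental injury is not defined, and relatedness to the intervention plays no part in the exclusion.

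A note after the exclusions adds two things. First, "Medical and scientific judgment should be exercised in deciding whether expedited reporting is also appropriate in situations other than those listed above". Second, its closing sentence makes any adverse event serious if the investigator judges its signs or symptoms to have significant clinical impact.

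Section 10.2 says that "effects of treatment may increase the risk of exercise-related injuries and adverse effects". It answers with screening, monitoring in class by the physiotherapist, and an AE log.

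The SAP (Serious Adverse Events) reports SAEs together with all other AEs, and adds a case-by-case review by the PI for the trial report.

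**The concern.** The intervention is supervised aerobic and strengthening exercise for patients recovering from bowel surgery, some of them on chemotherapy. An accidental-injury exclusion suits background accidents that have nothing to do with the trial. Here, with no relatedness test, it also covers an admission for an injury sustained during the study exercise, which is a risk the protocol itself names.

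What is at stake is how soon the sponsor learns of such an admission, and whether it is labelled an SAE and given the PI's case review. A pilot asking whether this model of rehabilitation is acceptable, and rehearsing procedures for a larger trial, should handle that kind of event promptly and consistently.

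**Working it through.** There is no statistical figure to reproduce. The check traces one event through the text and then compares reporting intervals with the timetable.

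**Step 1: trace an admission for an injury sustained in class.**
- It meets the hospitalisation criterion in 6.7.7, so it would be due within 24 hours.
- It also meets the accidental-injury exclusion, which contains no exception for it. It moves to the AE log and the annual listing.
- The judgement clause covers situations other than those listed above it. The exclusions are themselves listed above it, so its reach is unclear, and it is discretionary.
- The closing sentence could make the event an SAE again. It depends on the investigator's judgement, and 6.7.7 does not say whether it or the exclusion prevails.
- If the injury causes death or persistent disability, it is serious on those grounds. The exclusion covers hospitalisation only.

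**Step 2: timing.** Inputs are the 24-hour window and the annual listing (6.7.7), Phase 2 recruitment in months 8 to 13, classes in months 9 to 16 (section 12.2.3), and a 21-month study (section 8). The listing date is not given.

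- Length of class delivery: 16 − 9 + 1 = 8 months, shorter than the 12-month listing interval. At most one listing date can fall within it. Of 12 possible listing months, 8 fall within class delivery and 12 − 8 = 4 do not.
- Assumption A: listings run from study month 1, at the ends of months 12 and 24. An injury in month 9 is listed at the end of month 12, during recruitment. An injury early in month 13 waits until the end of month 24. That is 12 months later, 24 − 16 = 8 months after the last class, and beyond month 21.
- Assumption B: a listing falls at the end of month 8 and the next at the end of month 20. An injury early in month 9 waits 12 months. It is listed 20 − 13 = 7 months after recruitment closes and 20 − 16 = 4 months after the last class.

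The delay therefore runs from short to about 12 months, depending on a date the protocol does not state.

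**Step 3: how many patients.** The planned Phase 2 intervention group is 13 + 13 + 7 = 33 (section 6.2.3). The documents give no injury rate, so the expected number of such admissions cannot be calculated.

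**Step 4: what the SAP would still show.** A logged injury is coded and tabulated by System Organ Class and Preferred Term (Adverse Events), in tables with a column per arm (Summary of Study Data). What may be lost is the SAE label and the PI's review.

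**Step 5: a related gap.** The SAE outcomes omit life-threatening events, although the note beneath uses that term. An event that is life-threatening but leads to no admission, death or disability is left to judgement.

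**The case against.** The strongest counter-argument is the closing sentence of the 6.7.7 note. It applies to any adverse event, it defines seriousness, and it comes after the exclusions. An investigator could readily use it for an injury needing admission. That makes the gap less than absolute, but it does not close it, because precedence is unstated and the route depends on individual judgement.

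The section also commits to a trials SOP with expedited reporting as required, and introduces its own SAE list as particular cases. The SOP's content is not in the documents, so it cannot be assumed to undo a specific exclusion.

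A reader might infer more than the documents support:

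- **That the trial could not react to exercise harm.** The physiotherapist monitors the class and decides whether a patient continues, an AE log runs throughout, local incident systems operate, and the Clinical Trials Unit oversees AE reporting. Prompt notice to the sponsor is what is affected.
- **That the SAE comparison would be biased in favour of the intervention.** The SAP specifies no separate SAE comparison, and logged injuries remain visible by arm.
- **That section 10.2 names falls or fractures, or ranks injury as the main serious harm.** It speaks only of exercise-related injuries and adverse effects. Its monitoring examples are chest pain and extreme breathlessness, and admissions for those stay within 24-hour reporting.
- **That the steering group's three meetings compound the delay.** None is scheduled during Phase 2 classes, but the group is advisory and is not made the route for SAEs.

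The timing objection also stands in part: 12 months is a worst case, and under assumption A some injuries would be listed during recruitment.

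**Conclusion.** The gap is real but limited. Followed as written, 6.7.7 allows an admission for an injury caused by the study exercise to bypass 24-hour reporting, reach the sponsor only in an annual listing, and miss SAE classification and the PI's review. This holds unless the investigator invokes the closing sentence and that sentence is taken to prevail. The delay could be up to about 12 months, against 8 months of Phase 2 classes.

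The conclusion assumes that accidental injury carries its ordinary meaning and that the SOP does not override the exclusion. It concerns speed of notice and classification only. It does not show that injuries would go unrecorded, that deaths or lasting disability would be missed, or that the AE tables would be biased. The change is worth making because exclusion and named risk meet in the same intervention, and the procedures are being rehearsed for a larger trial. The life-threatening omission is secondary.

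**What to change.** Amend section 6.7.7 in three places:

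1. Limit the exclusion to hospitalisation for assault, or for accidental injury assessed as unrelated to study exercise or study assessments, in either arm. For controls, study exercise should include exercise taken up on the advice of the study booklet, which has a section on staying fit. Without this, the exception would apply almost wholly to the intervention arm and make SAE classification uneven.
2. State that the closing SAE sentence takes precedence over the exclusions.
3. Add life-threatening events to the SAE outcomes, to match the note below the list.

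The cost is a short protocol amendment, a relatedness assessment for each injury admission, and a few extra expedited reports. The SAP describes delivery of the intervention in the past tense. If classes have already finished, the wording serves the larger trial, and the step still open is for the PI's case review to cover any injury admissions held in the AE log.

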6.8 Analysis

All qualitative data will be analysed in order to address Objectives 1 to 4 and 10. Audio-recorded interviews will be transcribed verbatim. Transcripts will be analysed thematically using the Framework approach [55], which is a rigorous method that provides a structure within which qualitative data are organised and themes within and between groups of participants (e.g. between patients and clinicians) identified. Inter-rater reliability will be performed between the

researchers conducting analysis. From quantitative data we will generate the following: estimates of eligibility, consent, recruitment and retention rates and speed of recruitment (Objective 5); estimates of completion rates of study assessment tools (Objective 7); estimates of contamination between intervention and control groups (Objective 6); estimates of intervention fidelity (Objective 9). Descriptive presentations of the proposed primary and secondary outcomes will also be made to inform a sample size calculation for a large scale trial and decisions as to whether their inclusion would be informative in a future trial (Objective 8). Finally, comparisons between intervention sites on recruitment, retention and likely health outcomes etc. will be made to inform development of intervention and main trial components for a future large-scale trial.

6.9 Economic evaluation (Obj. 4 and 11)

Following previous research on the economics of cardiac rehabilitation [56], the economic evaluation will involve three main components: assessment of costs of the rehabilitation programme itself; estimation of further impacts on health care use; and bringing these two elements of cost together with data on outcomes described above.

6.9.1 Rehabilitation programme costs

Costs attributed to the rehabilitation programme for cancer will be borne by the NHS and by patients. NHS programme costs will be estimated on a per patient basis as the sum of costs of space rental, equipment (amortised over usual estimates of life cycles for such items), staff costs (using NHS wage rates in programme sites) and other programme consumable items (such as rehabilitation literature, again to be estimated from cost data at local programme sites). At local programme sites, we will interrogate financial records as well as interview finance and care staff, in order to assess actual impacts of providing the programme on the costs listed above – space and equipment provision, staff costs and any consumable items used. These data will also provide a basis for making further assumptions about cost impacts in other geographical locations.

Information to be obtained on patient-borne costs will be obtained by embedding questions in the data collection instrument to be administered with patients at the end of the programme about: (i.e. in a one-off schedule devised for their last interview). This will cover: distances travelled; transportation types; shoes, clothing and other equipment purchased to participate; child care expenses; and total time attending the programme. Where relevant, we will also ask patients to estimate actual monetary costs incurred by them for using or purchasing these items, but otherwise will impute data on prices of such items where respondents cannot recollect monetary amounts.

Finally, the programme involves building on a pre-existing cardiac rehabilitation programme, it will be important to assess impacts on the above NHS costs 'at the margin'; that is, in terms of what are the additional impacts on space, equipment, staff and consumables as a result of making use of a pre-existing programme. Again, this can be done by observing such impacts on the costs of such services at the local participating sites.

6.9.2 Further impacts on health care use

At each assessment with patients in both rehabilitation and usual care groups, we will ask them to report on: general practitioner visits; hospital emergency department visits and hospital admissions; visits to allied health departments such as physiotherapy and occupational therapy, nutrition, social work and vocational rehabilitation. Patients will also be asked to report on any medications used. A schedule of relevant items will be constructed about which we will ask questions on frequency of use in the previous three months (to match times of regular follow-up proposed in the main trial. Data on hospital visits and drug use will also be available through NHS records. The above items will be costed at NHS pay and prices or, where appropriate, using other (e.g. market-based) sources. Data on rehabilitation programme costs and those on further impacts will be aggregated and the statistical significance of differences in cost per patient between intervention and control group assessed by appropriate methods depending on the distributional characteristics of the data.

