6.6 Data collection for Feasibility study (Phase 1)

The purpose of the feasibility study is to evaluate and refine the intervention and main components of the trial. To meet Phase 1 study objectives we will carry out the following: cardiac rehabilitation physiotherapists will firstly attend a one-day training course delivered by a cancer-exercise specialist and complete an evaluation form about the

training. Then in one research site (Stirling), 12 cancer patients will be screened, recruited and referred for rehabilitation. The proposed outcomes and processes will be measured using the instruments we aim to use in a larger scale trial. Patients will be allocated to the next available rehabilitation class, which means that all 12 cancer patients are unlikely to attend the same classes. Patients will then attend a 10 week rehabilitation programme in a cardiac rehabilitation setting. A screening and recruitment log will be completed by a researcher to document all patients considered for the study and subsequently included or excluded at each stage of the recruitment process and reasons given. This will include information such as; when the patient was given information about the study, referred to cardiac rehabilitation, attended for clinical/risk assessment, and received an offer to attend rehabilitation classes. A researcher will also complete an intervention record log to document the number of classes attended by participants, type and duration of exercises, and which education classes the patient attended. On completion of rehabilitation, semi-structured face-to-face interviews will be conducted with, i) 12 cancer patients and a nominated family member, ii) 6 cancer and 6 cardiac clinicians who were involved in screening, recruitment, referral and/or delivering the intervention, and iii) 6 cardiac patients involved in the mixed cancer/cardiac patient rehabilitation classes, in order to gather responses about the acceptability of the intervention and trial procedures. Further description about data collection for Phase 1 is provided below.

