6.6.2 Screening and recruitment of cancer patients

- 1. Potential recruits will be identified from existing patients at follow up. All colorectal cancer patients who have completed surgery will be screened by a colorectal cancer Clinical Nurse Specialist at the first follow up appointment following surgery (approximately 6 weeks from date of surgery) to assess if it is safe for them to engage in physical activity from a cancer clinical perspective. The clinician will assess if there are contraindications to exercise due to cancer and late effects of treatment (e.g. patients with severe anaemia or with compromised immune function). At the follow up clinic, the nurse will give eligible patients an information sheet about the study and talk them through it. If the patient agrees to participate the nurse will refer the patient to cardiac rehabilitation by email, fax or letter and advise the patient that the cardiac rehabilitation service will contact them. Patients who decline to participate having read the study information will be asked if they would be willing to complete a questionnaire about reasons for declining to participate.
- 2. A member of the cardiac multi-disciplinary team (e.g. cardiac physiotherapist or nurse) will contact cancer patients and invite them to attend a cardiac rehabilitation clinical /risk stratification assessment to determine whether the patient will be able to safely exercise from a cardiac clinical perspective and plan physical activity goals tailored to individual patient needs. Patients who are deemed safe to exercise will be invited to attend cardiac rehabilitation classes. Patients who decline to attend a clinical /risk stratification assessment will be asked if they would be willing to complete a questionnaire about reasons for declining to participate.

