6.7.3 Randomisation

Patients will be randomised to the intervention or control group after they have consented to participating in the study and after baseline primary and secondary measures have been collected. Randomisation with stratification by centre will be conducted by Tayside Clinical Trials Unit.

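### The fixed three-month recall of health-care use fits T1 to T2 but not T0 to T1, so the between-arm cost comparison can take in unequal amounts of pre-randomisation use

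*Protocol*

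**What the plan says.** Protocol section 6.9.2 opens its list of GP, emergency, hospital and allied-health contacts with "At each assessment with patients in both rehabilitation and usual care groups, we will ask them to report on". The schedule consists of "questions on frequency of use in the previous three months (to match times of regular follow-up proposed in the main trial". The reason given for the window is therefore the future trial's follow-up, not this pilot's visits.

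This pilot's visits are set in section 6.7.5: "T1 - at the end of the intervention (data will be collected 12 weeks after baseline for patients in the control arm"), with T2 three months after T1. The intervention is "An 8/12-week (number of weeks depending on research site) post-hospital rehabilitation programme" (section 6.4). The protocol does not say which site runs which length, nor how long a patient may wait between randomisation and the first class. Randomisation takes place "after baseline primary and secondary measures have been collected" (section 6.7.3), so anything before T0 is also before randomisation.

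On use of the data, section 6.9.2 states: "Data on rehabilitation programme costs and those on further impacts will be aggregated". The between-arm difference in cost per patient is then to be tested. The same section notes that NHS records will also be available for hospital visits and drug use. The SAP, under Secondary Efficacy Analyses, leaves service use to the health economics team and gives no rule for it.

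**The concern.** A fixed look-back measures follow-up use correctly only if it equals the time since the previous assessment. If it is longer, it picks up use from before baseline; if shorter, some follow-up weeks are never asked about. Here the interval to T1 can differ between arms within a site, so the error need not cancel. Stratifying randomisation by centre does not help, because controls are seen at 12 weeks at every site while intervention patients are seen when their site's programme ends.

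The affected quantity is central to Objective 11. Section 6.9.3 makes the preferred option depend on whether lower health-care use in the rehabilitation arm offsets programme cost. The costing tools are also under test (Objective 4) and are meant to shape data collection in the larger trial, so an uncorrected window could be carried forward.

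**Working it through.** The plan gives no figure to reproduce, so the check is arithmetic on its time windows.

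**Inputs**
- Recall window R: three months = 365.25/12 × 3/7 = 13.04 weeks. Lower reading: 12 weeks, because section 12.2.3 costs a three-month span as 12 weeks.
- T1, control: 12 weeks after baseline (6.7.5).
- T1, intervention: programme length (8 or 12 weeks, 6.4) plus wait. The wait is not stated; 0 to 8 weeks is assumed.
- Planned patients per arm: Cardiff 13, Stirling 13, Inverness 7, total 33 (6.2.3).
- k = weekly use before baseline divided by weekly use after it. The documents give no rate, so k is assumed and varied.

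**Step 1: window against interval.** Weeks before baseline = max(R − T1, 0). Weeks uncounted = max(T1 − R, 0). Values for R = 12 are in brackets.

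| Arm, programme, wait | T1 (weeks) | Before baseline | Uncounted |
|---|---|---|---|
| Control | 12 | 1.04 (0) | 0 (0) |
| 8 weeks, wait 0 | 8 | 5.04 (4) | 0 (0) |
| 8 weeks, wait 2 | 10 | 3.04 (2) | 0 (0) |
| 8 weeks, wait 4 | 12 | 1.04 (0) | 0 (0) |
| 8 weeks, wait 8 | 16 | 0 (0) | 2.96 (4) |
| 12 weeks, wait 0 | 12 | 1.04 (0) | 0 (0) |
| 12 weeks, wait 2 | 14 | 0 (0) | 0.96 (2) |
| 12 weeks, wait 4 | 16 | 0 (0) | 2.96 (4) |

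At an 8-week site with no wait, 5.04/13.04 = 39% of the intervention patient's window lies before baseline. The excess over control is 4 weeks on either reading of three months.

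**Step 2: arm mean, no wait.** Intervention mean m = 1.04 + 4 × (share of the arm at 8-week sites).
- Smallest case, one 8-week site (the 7-patient site): 1.04 + 4 × 7/33 = 1.89 weeks.
- Largest case, two 8-week sites (both 13-patient sites): 1.04 + 4 × 26/33 = 4.19 weeks.
- Control: 1.04 weeks.

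**Step 3: T1 ratio when there is no true difference.** Ratio = [R + m(k − 1)] / [R + 1.04(k − 1)], with R = 13.04.
- k = 1: 1.00.
- k = 2: 14.93/14.08 = 1.06 to 17.23/14.08 = 1.22.
- k = 3: 16.82/15.12 = 1.11 to 21.42/15.12 = 1.42.
- k = 0.5: 12.10/12.52 = 0.97 to 10.95/12.52 = 0.87.

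**Step 4: add the matched T2 window** (13.04 weeks in each arm).
- k = 2: 27.97/27.12 = 1.03 to 30.27/27.12 = 1.12.
- k = 3: 29.86/28.16 = 1.06 to 34.46/28.16 = 1.22.

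**Step 5: observation time.** With no wait at an 8-week site, T0 to T2 is 8 + 13.04 = 21.04 weeks in the intervention arm and 12 + 13.04 = 25.04 weeks in control. Correcting the recall wording alone would leave this difference.

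**The case against.** Five arguments weigh against the point.

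1. *The window is a deliberate rehearsal of the main trial, in a pilot not powered for effect.* That explains the choice and lowers the stakes, but a between-arm cost test is still planned on these data.
2. *The trouble is mostly unequal T1 timing.* Largely true: the control arm's own mismatch is 0 to 1 week, and T1 to T2 fits. But the fixed window is what turns unequal timing into counted pre-randomisation use.
3. *The size is a corner case.* This stands in part. At a 12-week site with no wait, or an 8-week site with about a 4-week wait, the arms agree. The wait could be short, since section 6.7.2 reuses recruitment steps in which a class place is offered before consent. It could be longer, since section 6.7 places referral after randomisation. A T1 beyond 12 weeks is nowhere stated.
4. *The direction is not known.* This stands. Patients may be on adjuvant chemotherapy (6.2.1), so later use could exceed earlier use, which pushes the ratio below 1.
5. *NHS records could date hospital visits and drug use.* This stands, and leaves mainly GP and allied-health visits exposed. The protocol says records are also available, not that they replace recall.

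Two stronger readings are tempting. One is that T0 recall is added into follow-up cost, so that some use is counted twice. Section 6.9.2 does not say so; it is silent on whether T0 enters the total. The other is that the index operation contaminates follow-up cost. Screening is at the "first follow up appointment following surgery (approximately 6 weeks from date of surgery"), and T0 comes later, after referral, assessment and consent. T1 recall goes back at most about 5 weeks before T0, so it should not reach the operation. T0 recall might, but it precedes randomisation and is balanced between arms in expectation.

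**Conclusion.** The mismatch between the recall window and the T0 to T1 interval follows from the protocol's own timings, and neither document trims it. Its existence is firm; its size and sign are not. With no wait, one or two 8-week sites, the planned 13/13/7 allocation and no true difference, the spurious T1 ratio is about 1.06 to 1.22 for k = 2 and 1.11 to 1.42 for k = 3. It is smaller once T2 is included and below 1 if use before baseline is the lower. A T1 later than about 13 weeks would instead leave weeks uncounted.

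A reader might infer that the recall always inflates intervention cost, or that it makes the economic evaluation unusable. The documents support neither: the wait, the site lengths and the use rates are not given, and records cover part of the data. The point is worth correcting because a stated rule gives the wrong window for a planned comparison, and the correction is cheap.

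**What to change.** In the resource-use schedule and section 6.9.2:

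- At T1 and T2, ask about use 'since your last assessment on [date]'. This brings weeks before baseline and weeks uncounted to zero in both arms.
- State that T0 three-month recall is a baseline covariate only and is not added to follow-up cost.
- Limit NHS-record data on hospital visits and drugs to the dates from randomisation through T2.
- Compare arms over a common time horizon from randomisation. Where recalled counts carry no dates and cannot be cut at that horizon, use cost per week observed, and note that this assumes a roughly constant rate. This step is needed because observation can still be about 21 weeks against 25.
- State the programme length at each site, and reconcile the 8/12-week description in section 6.4 with section 6.6, which says of Stirling: "Patients will then attend a 10 week rehabilitation programme in a cardiac rehabilitation setting". Record the date of the first class so that the wait is known.

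The cost is one change of question wording and a few sentences in section 6.9.2. Recall becomes slightly longer than three months when T1 is delayed. The main trial's fixed wording is then rehearsed only at T0, although the T1 to T2 interval is still three months.
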